10.5. Appendix 5. Amyotrophic Lateral Sclerosis Assessment Questionnaire

The following is an example of the ALSAQ-40

Please complete this questionnaire as soon as possible. If you have any difficulties filling in the questionnaire by yourself, please get someone else to help you with it. However, it is your responses that we are interested in.

The questionnaire consists of a number of statements about difficulties that you may have experienced during the last 2 weeks. There are no right or wrong answers: your first response is likely to be the most accurate for you. Please tick the box which best describes your own experience or feelings.

Please try to answer every question even though some may seem rather similar to others or may not seem relevant to you.

All the information you give will be treated in the strictest confidence.

The following statements all refer to difficulties that you may have had **during the last 2 weeks**.

Please indicate, by ticking the appropriate box, how often the following statements have been true for you.

The following statements all refer to certain difficulties that you may have had during the last 2 weeks. Please indicate, by ticking the appropriate box, how often the following statements have been true for you.

*If you cannot walk at all
please tick Always/cannot walk at all.*

How often during the last 2 weeks have the following been true?

Please tick one box for each question

	Never	Rarely	Sometimes	Often	Always or cannot walk at all
1. I have found it difficult to walk short distances, e.g. around the house.					
2. I have fallen over while walking.					
3. I have stumbled or tripped while walking.					
4. I have lost my balance while walking.					
5. I have had to concentrate while walking.					

***Please make sure that you have ticked one box for each question
before going to the next set of questions***

The following statements all refer to certain difficulties that you may have had during the last 2 weeks. Please indicate, by ticking the appropriate box, how often the following statements have been true for you.

*If you cannot do the activities at all
please tick Always/cannot do at all.*

How often during the last 2 weeks have the following been true?

Please tick one box for each question

	Never	Rarely	Sometimes	Often	Always or cannot do at all
6. Walking has tired me out.					
7. I have had pains in my legs while walking.					
8. I have found it difficult to go up and down stairs.					
9. I found it difficult to stand up.					
10. I have found it difficult to get myself up out of chairs.					

***Please make sure that you have ticked one box for each question
before going to the next set of questions***

The following statement all refer to certain difficulties that you may have had during the last 2 weeks. Please indicate, by ticking the appropriate box, how often the following statements have been true for you.

*If you cannot do the activities at all
please tick Always/cannot do at all.*

How often during the last 2 weeks have the following been true?

Please tick one box for each question

	Never	Rarely	Sometimes	Often	Always or cannot do at all
11. I have had difficulty using my arms and hands.					
12. I have found turning and moving in bed difficult.					
13. I have found picking up things difficult.					
14. I found holding books and newspapers, or turning pages, difficult.					
15. I have difficulty writing clearly.					

**Please make sure that you have ticked one box for each question
before going to the next set of questions**

The following statement all refer to certain difficulties that you may have had during the last 2 weeks. Please indicate, by ticking the appropriate box, how often the following statements have been true for you.

*If you cannot do the activities at all
please tick Always/cannot do at all.*

How often during the last 2 weeks have the following been true?

Please tick one box for each question

	Never	Rarely	Sometimes	Often	Always or cannot do at all
16. I have found it difficult to do jobs around the house.					
17. I have found it difficult to feed myself.					
18. I have had difficulty combing my hair or cleaning my teeth.					
19. I have had difficulty getting dressed.					
20. I have difficulty washing the hand basin.					

**Please make sure that you have ticked one box for each question
before going to the next set of questions**

The following statement all refer to certain difficulties that you may have had during the last 2 weeks. Please indicate, by ticking the appropriate box, how often the following statements have been true for you.

*If you cannot do the activities at all
please tick Always/cannot do at all.*

How often during the last 2 weeks have the following been true?

Please tick one box for each question

	Never	Rarely	Sometimes	Often	Always or cannot do at all
21. I have had difficulty swallowing.					
22. I have had difficulty eating solid foods.					
23. I have found it difficult to drink liquids.					
24. I have found it difficult to participate in conversations.					
25. I have felt that my speech has not been easy to understand.					

**Please make sure that you have ticked one box for each question
before going to the next set of questions**

The following statement all refer to certain difficulties that you may have had during the last 2 weeks. Please indicate, by ticking the appropriate box, how often the following statements have been true for you.

*If you cannot do the activities at all
please tick Always/cannot do at all.*

How often during the last 2 weeks have the following been true?

Please tick one box for each question

	Never	Rarely	Sometimes	Often	Always or cannot do at all
26. I have slurred or stuttered while speaking.					
27. I have had to talk very slowly.					
28. I have talked less than I used to do.					
29. I have been frustrated by my speech.					
30. I have felt self-conscious about my speech.					

**Please make sure that you have ticked one box for each question
before going to the next page**

The following statement all refer to certain difficulties that you may have had during the last 2 weeks. Please indicate, by ticking the appropriate box, how often the following statements have been true for you.

How often during the last 2 weeks have the following been true:

Please tick one box for each question

	Never	Rarely	Sometimes	Often	Always
31. I have felt lonely.					
32. I have been bored.					
33. I have felt embarrassed in social situations.					
34. I have felt hopeless about the future.					
35. I have worried that I am a burden to other people.					

Please make sure that you have ticked one box for each question before going to the next set of questions

The following statement all refer to certain difficulties that you may have had during the last 2 weeks. Please indicate, by ticking the appropriate box, how often the following statements have been true for you.

How often during the last 2 weeks have the following been true:

Please tick one box for each question

	Never	Rarely	Sometimes	Often	Always
36. I have wondered why I keep going.					
37. I have felt angry because of the disease.					
38. I have felt depressed.					
39. I have worried about how the disease will affect me in the future.					
40. I have felt as if I have no freedom.					

Please make sure that you have ticked one box for each question.

[figure not shown]
Thank you for completing this questionnaire.

10.6. Appendix 6. Patient Global Impression of Change and Clinical Impression of Change**PGIC Scale:**

Since beginning treatment at this clinic, how would you describe the change (if any) in activity limitations, symptoms, emotions, and overall quality of life, related to your painful condition? (tick ONE box)

No change (or condition has got worse)		1
Almost the same, hardly any change at all		2
A little better, but no noticeable change		3
Somewhat better, but the change has not made any real difference		4
Moderately better, and a slight but noticeable change		5
Better, and a definite improvement that has made a real and worthwhile difference		6
A great deal better, and a considerable improvement that has made all the difference		7

In a similar way, please circle the number below, that matches your degree of change since beginning care at this clinic:

Clinical Impression of Change Scale

1. CGIC - Global Improvement: Rate total improvement whether or not, in your judgement, it is due entirely to drug treatment.

Compared to his/her condition at admission to the project, how much has he/she changed?

0 = Not assessed	4 = No change
1 = Very much improved	5 = Minimally worse
2 = Much improved	6 = Much worse
3 = Minimally improved	7 = Very much worse

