8.2.3.2. Patient Global Impression of Change

The Participant's impression of change at Days 240 and 365/ET will be measured with the PGIC questionnaire through use of the ePRO. This questionnaire measures the Participant's perception

of their level of activity, symptoms, emotions, and overall quality of life during the study. Each descriptor is ranked on a 10-point scale, where Much Worse = 0, No Change = 5, and Much Better = 10. The PGIC questionnaire is presented in Section [10.6](#), Appendix 6.

Upon completion of the questionnaire by the Participant, the study coordinator will check the questionnaire for completeness. Any omissions or ambiguous answers will be clarified by the Participant prior to leaving the clinic.

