3.2 Exploratory Endpoints

- Change from Baseline (Study VMALS-002-2 Day 0) in total mean Revised Amyotrophic Lateral Sclerosis Function Rating (ALSFRS-R) scores at Day 365 for Engensis compared to Placebo
- Change from Baseline (Study VMALS-002-2 Day 0) in ALSFRS-R subscores for Fine and Gross Motor Functions (sum of scores for items 4 to 9) and for Bulbar Function (sum of scores for items 1 to 3) at Day 365 for Engensis compared to Placebo
- Changes in the slope of the total ALSFRS-R score over time for Engensis compared to Placebo
- Change from Baseline (Study VMALS-002-2 Day 0) in muscle strength assessed bilaterally by Handheld Dynamometry (HHD) in muscles in the upper and lower extremities at Day 365 for Engensis compared to Placebo
- Change from Baseline (Study VMALS-002-2 Day 0) in Quality of Life (QoL) using the ALS Assessment Questionnaire (ALSAQ; with 40 items, ALSAQ 40) on Day 365 for Engensis compared to Placebo
- Patient Global Impression of Change (PGIC) and Clinical Global Impression of Change (CGIC) at Day 365 for Engensis compared to Placebo
- Change from Baseline (Study VMALS-002-2 Day 0) in Slow Vital Capacity (SVC) at Day 365 for Engensis compared to Placebo
- Time to tracheostomy for Engensis
- Time to all-cause mortality compared to Placebo

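### PGIC and CGIC have no single, dated reference point, so Day 365 ratings may cover different intervals and may not match the Day 0-anchored endpoints

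*Protocol*

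**What the plan says.** Four descriptions of the reference point appear in the protocol:

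- Section 8.2.3.2 says the PGIC measures the participant's perception "of their level of activity, symptoms, emotions, and overall quality of life during the study".
- The first item of the PGIC form (Section 10.6, Appendix 6) asks: "Since beginning treatment at this clinic, how would you describe the change (if any) in activity limitations, symptoms, emotions, and overall quality of life".
- The second item of the PGIC form asks for the number "that matches your degree of change since beginning care at this clinic".
- The CGIC form, in the same appendix, asks: "Compared to his/her condition at admission to the project, how much has he/she changed".

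Section 8.2.3.3, which describes the CGIC, gives no reference point.

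SAP 3.2 defines the endpoint as "Patient Global Impression of Change (PGIC) and Clinical Global Impression of Change (CGIC) at Day 365 for Engensis compared to Placebo", with a visit but no starting date. The neighbouring endpoints do have one, for example "Change from Baseline (Study VMALS-002-2 Day 0) in Slow Vital Capacity (SVC) at Day 365 for Engensis compared to Placebo". ALSFRS-R and HHD are worded the same way. ALSAQ-40 is anchored to Day 0 in the protocol, and the SAP adds the name of the parent study. SAP 6.15.4 summarises the PGIC and CGIC ratings descriptively by visit and treatment group.

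**The concern.** For ALSFRS-R or SVC, the analyst subtracts a recorded baseline, so the SAP's baseline definition (6.2.2) fixes the interval. A global impression of change is different. The rater makes the comparison mentally, against whatever starting point the question suggests, and nothing in the analysis can move that starting point afterwards.

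The design makes the wording matter. VMALS-002-2b is a separate protocol with its own consent. Its visit timing starts at the end of the Day 180 visit of VMALS-002-2, and no treatment is given in it. A rater asked about admission to a project could reasonably think of entry to the extension or of entry to the parent trial. A participant asked about the start of care at a clinic that also manages their ALS could think of a visit before either.

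Two people following the documents could then score different intervals, and both ratings would enter the same summary for that instrument. A rating that starts at Day 180 cannot register a change that arose while injections were being given. It would also sit in the report beside functional, strength, respiratory and quality-of-life changes counted from Day 0. The PGIC form adds to the doubt: it asks about a painful condition, which suggests that it was not adapted to this trial.

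**Working it through.** The plan attaches no sample size, power or error rate to these endpoints, so there is no stated figure to reproduce. The check sets the wordings side by side and then counts days.

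**Inputs**
- Extension start: nominal Day 180 (Protocol 1.1, study and treatment duration).
- PGIC and CGIC visits: Days 240 and 365, each with a window of ±7 days (Protocol 1.3).
- Treatment in the extension: none (Protocol 1.1 and Section 6).
- Parent-study visits labelled pre-dose: Days 0, 60 and 120 (SAP 6.15.6).

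**Step 1: what each wording can mean**

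| Place | Reference point in the text | Readings it allows |
|---|---|---|
| Protocol 8.2.3.2 (PGIC) | the study | literally the extension; possibly both studies together |
| PGIC form, item 1 | start of treatment at the clinic | most naturally the start of treatment in VMALS-002-2, because the extension has none |
| PGIC form, item 2 | start of care at the clinic | VMALS-002-2 entry, or a clinic visit before the trial |
| CGIC form | admission to the project | VMALS-002-2 entry, or extension entry at about Day 180 |

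Neither document defines the project or links any of these phrases to a date. SAP 6.2.2 does not help, because it governs computed changes and not a comparison built into a question.

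**Step 2: days covered by the Day 365 rating**
- From Day 0: 365 days (358 to 372 with the window).
- From Day 180: 365 − 180 = 185 days (358 − 180 = 178 to 372 − 180 = 192).
- Ratio: 185 / 365 = 50.7% (178 / 358 = 49.7% to 192 / 372 = 51.6%).

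**Step 3: days covered by the Day 240 rating**
- From Day 0: 240 days. From Day 180: 240 − 180 = 60 days.
- Ratio: 60 / 240 = 25% (53 / 233 = 22.7% to 67 / 247 = 27.1%).
- This visit is summarised, but the named endpoint is at Day 365.

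**Step 4: dosing period**
- Of the three pre-dose visits (Days 0, 60 and 120), none falls between Day 180 and Day 365. The shorter reading contains 0 of 3; a Day 0 reading contains all three.

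**Step 5: start of care**
- If PGIC item 2 is read as the first visit to the clinic, its span exceeds 365 days by an amount the documents do not allow one to compute.

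**The case against.** The strongest case on the other side is that the intended reference is clear enough. The objective served by PGIC and CGIC concerns improvement following Engensis injections, and all injections were in VMALS-002-2. The CGIC form asks about change whether or not it is due to drug treatment and adds a drug-effect index, which makes little sense for an untreated period. Participants keep the same number, so the project can be taken as the whole programme. The sentence in 8.2.3.2 describes the instrument and is not in the Appendix 6 question put to respondents. Site training and the actual ePRO screens are not among the documents, so it is unknown whether raters differ.

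Much of this stands. The objective shows what was meant, and it makes Day 0 the natural anchor. It does not put that anchor into the question the rater reads, and the CGIC phrase and PGIC item 2 remain open.

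Several stronger inferences should be resisted:

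- **That the ratings omit the dosing period.** This follows only if the CGIC reference, or the sentence in 8.2.3.2, is read as the extension. PGIC item 1 cannot sensibly mean Day 180.
- **That the SAP pools the two instruments.** It does not: they have separate tables (14.6.5 and 14.6.6) and listings. Any mixing is between raters within one instrument.
- **That the shorter span moves a rating by a category.** The documents give no mapping from functional loss to CGIC categories. On PGIC item 1, no change and any worsening share category 1, so a declining participant may score the same over either span.
- **That one arm is favoured.** Participants and investigators remain blinded (Protocol 6.1.2), so an unclear anchor adds noise with no evident direction.

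**Conclusion.** The point holds as a defect of endpoint definition. The documents give inconsistent, undated reference points for two instruments whose meaning depends on that reference. Under the shorter available reading of the CGIC, the Day 365 rating covers about half the interval used for the other change endpoints (185 of 365 days) and none of the listed pre-dose visits. PGIC item 2 may run longer than the trial. PGIC item 1 is the least doubtful.

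The size rests on a nominal Day 180 for extension entry and on the visit days as scheduled. Whether any rater actually used the shorter or longer reading cannot be known from the documents. With at most 18 participants, a few ratings over a different interval could visibly change an arm's distribution, but no frequency can be put on that.

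The consequence is limited to interpreting exploratory, descriptive endpoints. The primary safety analysis and any error rate are unaffected. This is a cheap improvement worth making, not a threat to the trial's conclusions.

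**What to change.** Use one anchor throughout: compared with just before the first study injection in VMALS-002-2 (Day 0). Put it in Protocol 8.2.3.2 and 8.2.3.3, in both PGIC items and the CGIC item of Appendix 6, and in the ePRO text. Word the endpoint in SAP 3.2 and its summary in 6.15.4 as change since VMALS-002-2 Day 0. This matches the other change endpoints and the objective's reference to the injections.

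Flag in the listings any rating collected under the current form wording, and state in the report which wording was shown. A separate sensitivity table is not needed; with no more than 18 participants over two arms it would add little.

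The cost is a wording amendment, an ePRO text update and a short note to sites. There are two drawbacks. Recall over a year is less exact than over six months. Ratings already collected keep their present anchor, so a change during the study leaves two wordings in the data, which is why the flag matters. The forms used in VMALS-002-2 are not in these documents, so comparability with any ratings made there should be checked before the text is changed.

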	Protocol Number:	VMALS-002-2b	
STATISTICAL ANALYSIS PLAN. PHASE 2-3-4			

1 INTRODUCTION

This is a Phase 2, 6-month extension study, multicenter study designed to assess the long-term safety of Engensis (containing the active pharmaceutical ingredient VM202) in Participants with ALS.

This document details the planned statistical analyses for the Helixmith Co., Ltd VMALS-002-2b study titled “A 6-Month Extension Study Following Protocol VMALS-002-2 (A Phase 2a, Double-Blind, Randomized, Placebo-Controlled, Multicenter Study to Assess the Safety of Engensis in Participants with Amyotrophic Lateral Sclerosis)”. This document covers all statistical analyses planned in the study.

The proposed analyses are based on the contents of the final protocol, version 1.1 (dated 12-OCT-2021).

2 STUDY OBJECTIVES

Primary Objective:

- To evaluate the long-term safety of intramuscular (IM) injections of Engensis in Participants with Amyotrophic Lateral Sclerosis (ALS)

Exploratory Objectives:

- To evaluate changes in muscle function following Engensis injections in ALS Participants
- To evaluate muscle strength changes following Engensis injections in ALS Participants
- To determine whether IM administration of Engensis has effects on respiratory function in ALS Participants
- To determine whether IM administration of Engensis has positive effects on survival in ALS Participants
- To evaluate Quality of Life improvement following Engensis injections in ALS Participants compared to Placebo
- To evaluate Patient and Clinical Reported Outcome improvement following Engensis injections in ALS Participants compared to Placebo

3 ENDPOINTS

3.1 Primary Endpoints

QMD Ref: Worldwide-TMP-ST-005-7.0 Effective: 12Aug2019	Governing QMD: Worldwide-SOP-ST-001
Confidentiality Statement	

This document is the property of Worldwide Clinical Trials Inc. and may not be duplicated, copied, altered or removed from company without prior approval from Worldwide Quality Assurance or in compliance with Worldwide Standard Operating Procedures.

Worldwide Clinical Trials Controlled Quality Management Document			
 WORLDWIDE CLINICAL TRIALS	Sponsor:	Helixmith Co., Ltd.	
	Protocol Number:	VMALS-002-2b	
STATISTICAL ANALYSIS PLAN. PHASE 2-3-4			

- Incidence of treatment-emergent adverse events (TEAEs), treatment-emergent serious adverse events (TESAEs), and adverse events of special interest (AESIs) for Engensis compared to Placebo
- Incidence of clinically significant laboratory values for Engensis compared to Placebo

3.2 Exploratory Endpoints

- Change from Baseline (Study VMALS-002-2 Day 0) in total mean Revised Amyotrophic Lateral Sclerosis Function Rating (ALSFRS-R) scores at Day 365 for Engensis compared to Placebo
- Change from Baseline (Study VMALS-002-2 Day 0) in ALSFRS-R subscores for Fine and Gross Motor Functions (sum of scores for items 4 to 9) and for Bulbar Function (sum of scores for items 1 to 3) at Day 365 for Engensis compared to Placebo
- Changes in the slope of the total ALSFRS-R score over time for Engensis compared to Placebo
- Change from Baseline (Study VMALS-002-2 Day 0) in muscle strength assessed bilaterally by Handheld Dynamometry (HHD) in muscles in the upper and lower extremities at Day 365 for Engensis compared to Placebo
- Change from Baseline (Study VMALS-002-2 Day 0) in Quality of Life (QoL) using the ALS Assessment Questionnaire (ALSAQ; with 40 items, ALSAQ 40) on Day 365 for Engensis compared to Placebo
- Patient Global Impression of Change (PGIC) and Clinical Global Impression of Change (CGIC) at Day 365 for Engensis compared to Placebo
- Change from Baseline (Study VMALS-002-2 Day 0) in Slow Vital Capacity (SVC) at Day 365 for Engensis compared to Placebo
- Time to tracheostomy for Engensis
- Time to all-cause mortality compared to Placebo

4 SAMPLE SIZE

The number of Participants in this study will be determined by the number who complete the Day 180 Visit in VMALS-002-2. The maximum potential Participants in VMALS-002-2b is 18, based on enrollment in VMALS-002-2.

5 RANDOMIZATION

Not applicable in this SAP.

QMD Ref: Worldwide-TMP-ST-005-7.0 Effective: 12Aug2019	Governing QMD: Worldwide-SOP-ST-001
Confidentiality Statement	

This document is the property of Worldwide Clinical Trials Inc. and may not be duplicated, copied, altered or removed from company without prior approval from Worldwide Quality Assurance or in compliance with Worldwide Standard Operating Procedures.

Worldwide Clinical Trials Controlled Quality Management Document			
 WORLDWIDE CLINICAL TRIALS	Sponsor:	Helixmith Co., Ltd.	
Protocol Number:			VMALS-002-2b
STATISTICAL ANALYSIS PLAN. PHASE 2-3-4			

